10.2 Concomitant therapy

Any concomitant therapy clinically required will be permitted. Contraindications are listed in section 4.3 of the relevant SmPCs. A list of drug interactions is detailed in section 4.5 of the relevant SmPCs for both drugs. Any concomitant therapies which interact with the trial drugs will be recorded. Potential drug interactions with concomitant medications should be managed as per standard clinical practice, including therapeutic drug monitoring as appropriate.

10.3 Accountability and dispensing

10.3.1 Pharmacy responsibilities

The IMP will be provided directly using standard hospital stock during inpatient stay (including use of ward stock where appropriate) with no requirement for trial-specific dispensing.

10.3.2 Drug accountability

Drug accountability is not required as the drug will be administered in line with routine standard care practices. Compliance will be measured using inpatient records.

11. Procedures and assessments

11.1 Participant identification

All patients who have been admitted to a hospital with a traumatic brain injury will be screened for eligibility. A member of the clinical team will assess the potential eligibility of these patients based on the inclusion/exclusion criteria outlined earlier in the protocol.

11.2 Consent

The REC must approve the Informed Consent Form (ICF) and must follow GCP, local regulatory requirements and legal requirements. The investigator or designee must ensure that each trial participant, or his/her legally acceptable representative, is fully informed about the nature and objectives of the trial and possible risks associated with their participation.

The investigator or designee will obtain written informed consent from each participant or the participant's legally acceptable representative before any trial-specific activity is performed. Once consent has been obtained, a copy of the signed ICF will be sent via secure transfer (e.g. nhs.net) to the trial coordination centre for verification that it has been completed correctly. The informed consent form used for this trial and any change made during the course of this trial must be prospectively approved by the REC. The investigator will retain the original of each participant's signed informed consent form.

Should a participant or participant's legal representative require a verbal translation of the trial documentation by a locally approved interpreter/translator, it is the responsibility of the individual investigator to use locally approved translators. A locally translated PIS may be provided if required.

Consent must be taken prior to trial randomisation

Where potential participants fulfil the eligibility criteria, they will be approached by a member of the research team who will provide the PIS and clarify any information from the potential participant which may preclude recruitment. Wherever possible, informed consent will be obtained from the potential participant; however, due to the nature of the condition, this may not be possible.

Patient legal representative available in the hospital

In potential participants lacking capacity, a legal representative will be sought. If the legal representative is available in the hospital, is contactable, or is due to visit the potential participant within a reasonable timescale, then they will be provided with information about the trial and asked if they will provide consent for the potential participant before enrolment. This will take place during their visit to the patient.

For the purposes of sites in England, Wales and Northern Ireland, a legal representative is defined as:

A person not connected with the conduct of the trial who is:

- a) Suitable to act as the legal representative by virtue of their relationship with the adult, and
- b) Available and willing to do so

For the purposes of sites in Scotland, a legal representative is defined as:

- a) Any guardian or welfare attorney who has the power to consent to the adult's participation in research
- b) If there is no such person, the adult's nearest relative as defined in section 87(1) of the Adults with Incapacity (Scotland) Act 2000

The patient's legal representative is not available in the hospital

Due to the condition of these patients, there will be those who will have no known legal representative or where the legal representative is not contactable or not able to visit the hospital at short enough notice to be able to enrol the potential participant within the required 72 hour time frame. In such cases, we advocate enrolment would be possible with written agreement from an independent clinician. If no legal representative is available for discussion, then an independent clinician (Independent Healthcare Professional) will be approached. If a legal representative visits the hospital later, then the trial will be discussed with them, and their consent sought at that time point to continue in the trial.

Participants who regain capacity whilst in the hospital will be informed about the clinical trial, and consent to continue will be sought. If, at any stage, either the legal representative or the participant chooses to withhold consent, then the participant will be withdrawn from the trial.

Participants who regain capacity following discharge will be contacted by phone and posted a PIS and ICF as soon as possible to complete and return to trial team.

Independent healthcare professional (IHP) definition

For the purposes of the TOP-TBI trial, the Independent Healthcare Professional (IHP) is defined as:

A person who is not connected with the conduct of the trial, specifically:

- a) The sponsor of the trial.
- b) A person who undertakes activities connected with the management of the trial.
- c) An investigator of the trial or,
- d) A health care professional who is a member of the investigator's delegated team for the purposes of the trial.

Any new information which becomes available, which might affect the participant's willingness to continue participating in the trial, will be communicated to the participant or participants personal legal representative as soon as possible, verbally if the participant is in hospital, by post if they have been discharged.

[figure not shown]

Figure 1: Consent flowchart.

11.3 Screening evaluation

11.3.1 Screening assessments

Trial-specific assessments will only be conducted after written informed consent (from the participant, the participant's legal representative or independent healthcare professional). Medical history precluding eligibility will be obtained from either the patient's case notes or after discussion with the potential participant (or the potential participant's representative, if available).

11.3.2 Participant registration / randomisation

Upon completion of consent and screening, participants will be enrolled on the TOP-TBI trial. A unique participant ID will be allocated to each participant using a computer randomisation system (Sealed Envelope).

A de-identified record of the patients approached, along with the numbers of, and reasons for, screen failures and refusal of consent, will be kept at each site on a Screening Log and reported to the Trial Coordinating Centre when requested. This information will be used to identify any barriers to recruitment and allow improvement measures to be identified and implemented in a timely manner.

Following randomisation, a letter will be sent to the participant's GP, informing them about the participant's participation.

11.4 Screening and Baseline Assessments

All participants will have a medical history taken and a clinical examination as part of the routine standard care. The following are to be recorded in the CRF:

- Inclusion/exclusion criteria review
- Informed consent process followed and consent or authorisation for enrolment obtained (signed consent form sent to the trial coordination centre for verification within 24 working hours)
- Routine review of clinical laboratory results
- ECG (if indicated by local policy)
- Standard of Care:
 - Patient medical history (including co-morbidities and relevant medications, including use of anticoagulation)
 - If pre-existing anticoagulation is present, the timing of any reversal agents used
 - Patient demography
 - Injury-related events - date of TBI, date of possible intubation, other injuries
 - Neurological status
 - Imaging review

11.5 Trial assessments

11.5.1 Timing of assessments

Participants will be monitored as per routine clinical practice until discharge and thereafter at 30 days (+/- 5 days), 90 days (+/- 15 days), 6 months and 12 months (+/- 1 month) to score clinical outcomes.

11.5.2 Assessments at time point

- Adverse events of special interest (AESI) during treatment and follow up timepoints up to 12 months. including major and clinically relevant bleeding events
- Asymptomatic DVT assessment with an ultrasound scan during hospital stay (*only relevant for all sites that perform screening ultrasound as part of routine clinical practice*)
- Assessment for VTE during hospital admission, 30 days and 90 days
- Progression of intracranial haemorrhage on routinely performed imaging within 14 days after randomisation requiring neurosurgical intervention
- Quality of life (EQ5D-5L) at Day 30 or discharge, 6 and 12 months
- Mortality at 7-days, 30 days and 12 months
- Glasgow Outcome Scale-Extended (GOS-E) at 6 and 12 months
- Length of stay of index admission
- Economic analysis at 12 months

Method of follow-up

Prospective follow-up data (at 30 days - primary endpoint), 90 days, 6- and 12-months post-enrolment) will be collected electronically via email or online formats such as Qualtrics or MS Forms or via postal questionnaires or telephone interviews by blinded study personnel if participants cannot complete forms electronically/return postal questionnaires. The questionnaires will include questions on any longer-term effects of VTE, the extended Glasgow Outcome Scale (GOSE, only 6 and 12 month FU) and EQ-5D-5L questionnaire (30 days, 6- and 12-month FU). Re-admission and out-patient data will be captured from Hospital Episode Statistics (HES) data.

11.5.3 Assessments at the end of trial

At the end of the trial, a health economic evaluation will be performed (details in section 16.5).

11.6 Table for schedule of assessments (Table 2)

	Screening/ Baseline (within 72 hours of TBI)	Treatment Phase (within 72 hours of TBI OR >120 hours of TBI)	Day 7	Day 14	Day 30 (+/- 5 days) OR Discharge	Follow up phase		
						Day 90 (+/- 15 days)	6 months (+/- 1 month)	12 months (+/- 1 month)
Eligibility assessment	X							
Informed consent	X							
Randomisation	X							
IMP administration		X						
Safety assessments (AESI/SARs)	X	X	X	X	X	X	X	X
Intracranial haemorrhage				X				
Mortality			X		X			X
VTE occurrence	X				X	X		
GOSE							X	X
EQ-5D-5L					X		X	X
Economic evaluation								X

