8.6 Trial outcome measures

8.6.1 Primary outcome measure

Clinically relevant VTE within 30 days from randomisation, including any confirmed diagnosis of symptomatic DVT, pulmonary embolism, or death related to VTE.

The definition of ***clinically relevant*** VTE is as follows:

- Any ***symptomatic*** DVT or PE event where the treating team has made a working diagnosis for a DVT or PE based on symptoms and or clinical signs and subsequently investigations requested to verify the diagnosis (e.g., ultrasound / CT pulmonary angiogram (CTPA)).

DVT or PE occurrence

Symptomatic DVT or PE will be investigated as per standard clinical practice either by compression Doppler ultrasound of the femoral and popliteal veins or CTPA, as appropriate.

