11.7 Long term follow-up assessments

Participants will be followed up for 12 months post-randomisation by questionnaire. Assessments will not necessarily require a face-to-face interview. Participants will be given the option of conducting assessments by email, postal mail (via return in a self-addressed, stamped envelope sent to their provided contact address e.g. home, rehabilitation centre), or by telephone. Follow up assessments may also be completed during routine clinic visits. If participants who are sent the follow-up questionnaires by email or postal mail do not return them after approximately 2 weeks, they will be contacted by telephone. If the time point after an assessment exceeds 8 weeks, and there is no response, every effort will be made to obtain required information via other means e.g. by contacting the next of kin, the patient's GP, local hospital or rehabilitation centre.

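### Table 2 lets the 30-day VTE check fall at discharge, against sections 11.5.1 and 11.5.2, and the minus-5-day window lets it precede day 30

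*Protocol*

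**What the plan says.** Protocol section 8.6.1 defines the primary outcome as "Clinically relevant VTE within 30 days from randomisation, including any confirmed diagnosis of symptomatic DVT, pulmonary embolism, or death related to VTE".

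The schedule in section 11.6 (Table 2) has one column headed "Day 30 (+/- 5 days) OR Discharge". VTE occurrence, mortality and EQ-5D-5L all carry a mark in it. The next VTE mark is at day 90, with a tolerance of 15 days either way.

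The text reads differently:

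- Section 11.5.1: "Participants will be monitored as per routine clinical practice until discharge and thereafter at 30 days (+/- 5 days), 90 days (+/- 15 days". Discharge ends routine monitoring, and the 30-day contact follows it.
- Section 11.5.2 lists "Assessment for VTE during hospital admission, 30 days and 90 days" and "Mortality at 7-days, 30 days and 12 months". Neither entry has a discharge alternative. In that list, as in section 8.6.2, only EQ-5D-5L may be taken at day 30 or at discharge.
- Section 11.5.2, Method of follow-up, labels the 30-day contact as the primary endpoint and adds: "Re-admission and out-patient data will be captured from Hospital Episode Statistics (HES) data".

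Section 15.1 analyses time to VTE with a Cox model and reports the absolute difference in 30-day VTE rates. The only reason it names for censoring before day 30 is dropout.

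**The concern.** There are two separate faults in the schedule.

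The first is a contradiction. A site working from Table 2 could complete its 30-day VTE form at discharge. A site working from sections 11.5.1 and 11.5.2 would make a further contact around day 30. Sites could then ascertain the primary endpoint over different lengths of time while each believes that it is following the protocol.

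The second is not a slip in the table, because text and table agree on it. The tolerance around day 30 runs from day 25 to day 35. A contact on day 25 is compliant, yet it cannot show what happens on days 26 to 30. VTE at 90 days has the same problem, since its contact may fall on day 75.

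Either would be harmless if the protocol said what happens next, but it does not. It neither requires a later check to day 30 nor says that follow-up is censored at the early contact. A participant seen as scheduled at discharge or on day 25 is not a dropout, so the censoring provision in section 15.1 does not plainly cover that person. At stake are the completeness of the primary endpoint and its comparability across sites. If discharge timing differed between arms, comparability of the arms would be at stake too.

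**Working it through.** **1. The passages side by side**

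| Item | Table 2 (11.6) | Text (11.5.1, 11.5.2) |
|---|---|---|
| VTE, first follow-up | day 25 to 35, or discharge | in hospital, and thereafter day 25 to 35 |
| EQ-5D-5L, first follow-up | day 25 to 35, or discharge | day 30 or discharge |
| VTE, second follow-up | day 75 to 105 | day 75 to 105 |

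The discharge alternative for VTE therefore rests on the shared column header alone. The early edge of the window (30 − 5 = 25; 90 − 15 = 75) stands in both places.

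**2. The plan's own sample size**

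Inputs from section 15.3: 10% vs 5%, 90% power, 5% level (taken as two-sided), equal arms. With p̄ = 0.075 and pooled variance under the null:

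n per arm = [1.960·√(2·0.075·0.925) + 1.282·√(0.10·0.90 + 0.05·0.95)]² / 0.05² = (0.7301 + 0.4752)² / 0.0025 = 581.1, so 582 per arm and 1164 in total, as stated.

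The same formula gives 1442 for 12% vs 7% (stated 1441). The calculation assumes that every 30-day event is seen. With 1441 evaluable participants, power is 95.1% for 10% vs 5% and 90.0% for 12% vs 7%.

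**3. Share of 30-day events that a day-25 contact cannot see**

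Assume exponential event times with median m, so F(t) = 1 − 2^(−t/m). The share missed is [F(30) − F(25)] / F(30). Section 9.3.2 cites a median of 6 days to VTE in critically ill trauma patients; 10 days is an assumed slower case.

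- m = 6: (0.96875 − 0.94432) / 0.96875 = 2.5%
- m = 10: (0.87500 − 0.82322) / 0.87500 = 5.9%

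**4. What that would cost in power, as an upper bound**

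Suppose every participant is contacted on day 25, nothing is recovered later, and both arms lose the same share. Multiply both rates by the share seen, c, with 720.5 per arm. For 10% vs 5% at m = 10, c = 0.9408 and the rates become 9.408% and 4.704%, a difference of 4.70 points. The null standard error is √(2·0.07056·0.92944/720.5) = 0.01349 and the alternative one is 0.01344. Power = Φ[(0.04704 − 1.960·0.01349)/0.01344] = 93.7%.

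| Share missed | 10% vs 5%: difference, power | 12% vs 7%: power |
|---|---|---|
| 0 | 5.00 points, 95.1% | 90.0% |
| 2.5% (m = 6) | 4.87 points, 94.5% | 89.2% |
| 5.9% (m = 10) | 4.70 points, 93.7% | 88.0% |

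**5. Contact at discharge**

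The same formula applies for any discharge day, and the share missed grows as that day gets earlier. The documents give no distribution of discharge days, so no figure can be derived from them.

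**The case against.** The strongest reply is that this is only a loosely worded column header. It does not say that the earlier of the two dates applies. Three statements in the text place VTE assessment at 30 days, one of them after discharge, and a sensible site would follow them. This stands to the extent that contact at discharge is not the settled plan; it is one side of a contradiction. It does not answer the minus-5-day window, on which text and table agree.

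The second reply is that later sources would catch what an early contact misses. Everyone has another VTE assessment between days 75 and 105, always after day 30. HES readmission and outpatient data are captured, and section 11.7 pursues non-responders through next of kin, GP, local hospital or rehabilitation centre. This also stands in part: post-discharge events are not shown to be lost. But nothing assigns these sources to completing 30-day VTE status, and the only analytic use stated for HES data is costing, in section 15.6.

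A reader might infer more than the documents support, in four ways:

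- *That an early contact is entered as event-free for the full 30 days.* No such rule is stated. A time-to-event analysis could equally censor at the contact. The protocol is silent.
- *That 30-day all-cause mortality is compromised too*, since it shares the column. Section 14.1.1 counts all deaths from randomisation to the 12-month follow-up, so 30-day status can be derived from dates of death.
- *That telephone reminders come too late*, because they start about two weeks after a questionnaire is not returned. A contact after day 30 does not cut the endpoint short if event dates are taken.
- *That a large fraction of events is lost at discharge.* Any such figure needs an assumed discharge day and no later recovery.

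**Conclusion.** The point holds as an inconsistency in the schedule together with an assessment window that opens too early for the primary endpoint. A site following Table 2 could stop 30-day VTE ascertainment at discharge. A site following either text or table could stop it on day 25. The protocol does not say how the remaining days are covered.

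The early window alone is a small problem: about 2.5% to 6% of 30-day events, and at most about 2 percentage points of power in the scenarios above. This assumes exponential event times with a median of 6 to 10 days, a day-25 contact for everyone, equal loss in both arms and no recovery. The 6-day median comes from critically ill trauma patients, whereas this trial also admits ward patients.

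The discharge option could matter more, but its size cannot be determined from the documents. If later contacts and linked data are used to complete status, some of either loss would be recovered. The correction is worth making because it protects the primary endpoint at very little cost.

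**What to change.** 1. Split the Table 2 column. Keep the discharge alternative for EQ-5D-5L only, as in sections 8.6.2 and 11.5.2.
2. For VTE, set the 30-day contact no earlier than day 30 (for example day 30 to day 44) and the 90-day contact no earlier than day 90. Ask about the whole period since randomisation and record the date of each event. Change section 11.5.1 to match.
3. State that the day-90 assessment and linked HES data are used to complete 30-day VTE status.
4. State in section 15.1 that anyone whose last VTE assessment is still before day 30 after that step is censored at that contact, in addition to censoring for dropout.

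The cost is schedule wording and two sentences on ascertainment and censoring. Some contacts move a few days later. Sites that had planned to close the VTE form at discharge will make one more contact, which section 11.5.1 already expects of them.

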11.7 Long term follow-up assessments

Participants will be followed up for 12 months post-randomisation by questionnaire. Assessments will not necessarily require a face-to-face interview. Participants will be given the option of conducting assessments by email, postal mail (via return in a self-addressed, stamped envelope sent to their provided contact address e.g. home, rehabilitation centre), or by telephone. Follow up assessments may also be completed during routine clinic visits. If participants who are sent the follow-up questionnaires by email or postal mail do not return them after approximately 2 weeks, they will be contacted by telephone. If the time point after an assessment exceeds 8 weeks, and there is no response, every effort will be made to obtain required information via other means e.g. by contacting the next of kin, the patient's GP, local hospital or rehabilitation centre.

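### The general chase rule in section 11.7 (telephone at about 2 weeks, other sources after 8 weeks) cannot meet the ±5-day window of the day-30 contact

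*Protocol*

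**What the plan says.** Section 11.5.1 sets the contacts after discharge: "thereafter at 30 days (+/- 5 days), 90 days (+/- 15 days), 6 months and 12 months (+/- 1 month) to score clinical outcomes". Table 2 (section 11.6) repeats the windows and heads the first of these columns as day 30 or discharge.

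Section 11.5.2, under the method of follow-up, puts the primary endpoint among the data gathered by questionnaire: "Prospective follow-up data (at 30 days - primary endpoint), 90 days, 6- and 12-months post-enrolment) will be collected electronically via email", or by other online formats, post or blinded telephone interview. The forms carry EQ-5D-5L at 30 days. On VTE, the same paragraph says: "The questionnaires will include questions on any longer-term effects of VTE".

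Section 11.7 then states: "Participants will be followed up for 12 months post-randomisation by questionnaire". Participants may choose email, post or telephone, and a routine clinic visit can also serve. For participants sent forms by email or post, the chase rule covers those who "do not return them after approximately 2 weeks, they will be contacted by telephone. If the time point after an assessment exceeds 8 weeks" with no response, the information is sought from next of kin, the GP, the local hospital or the rehabilitation centre. No exception is made for day 30.

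**The concern.** A chase rule should be able to recover a missing form before the window for that contact closes. Here the wait before the first chase (about 14 days) is longer than the whole day-30 window (days 25 to 35). A site that follows section 11.7 exactly will therefore miss the window in section 11.5.1 for every emailed or posted day-30 form that needs chasing.

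Two things are at stake:

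- **EQ-5D-5L.** It measures a state at a point in time. Table 2 shows no baseline value, so the day-30 or discharge value is the first input to the QALY calculation in section 15.6. A value obtained weeks later is not a day-30 value.
- **VTE between discharge and day 30.** The primary analysis in section 15.1 models time to VTE and so needs event dates. The next scheduled VTE check after day 30 is day 90. A chase that ends inside the day-90 window may date an event poorly or merge the two contacts, unless the date is taken from records. Section 15.3 itself notes that these patients often have lasting cognitive difficulties, so recall is a weak substitute.

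**Working it through.** The protocol gives no derived figure on this point to reproduce. The check is calendar arithmetic on its stated intervals.

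**Inputs**

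- Day-30 window: 30 ± 5, i.e. days 25 to 35 (11.5.1, Table 2).
- Day-90 window: "90 days (+/- 15 days"), i.e. days 75 to 105 (11.5.1).
- 6- and 12-month windows: ± 1 month. Taking 6 months as 183 days, 12 months as 365 days and a month as 30 days (my convention), these are days 153 to 213 and 335 to 395.
- First chase: send day + 14 (11.7, stated as approximate).
- Second chase: after send day + 56 (11.7).
- Send day: not stated. I tried the start, middle and end of the window.

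**Day-30 contact**

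| Form sent | Telephone (+14) | Days past day 35 | Other sources (+56) | Inside days 75–105? |
|---|---|---|---|---|
| Day 25 | Day 39 | 4 | after day 81 | yes |
| Day 30 | Day 44 | 9 | after day 86 | yes |
| Day 35 | Day 49 | 14 | after day 91 | yes |

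If the 8 weeks run from the nominal time point instead of the send date, the second step is 30 + 56 = day 86 in every row, still inside the day-90 window.

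**Can any send date rescue the rule?** For the call to fall by day 35 after a 14-day wait, the form must go out by 35 − 14 = day 21, which is before the window opens on day 25. Put the other way, the wait could be at most 35 − 30 = 5 days for a form sent on day 30, or 35 − 25 = 10 days for one sent on day 25.

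**The later contacts, form sent on the nominal date**

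- Day 90: 90 + 14 = 104, within 105.
- 6 months: 183 + 14 = 197, within 213.
- 12 months: 365 + 14 = 379, within 395.

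So the telephone step suits every contact except day 30.

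**The case against.** **Scope.** Section 11.7 is headed as long-term follow-up, and Table 2 as extracted places its follow-up phase over day 90, 6 months and 12 months, with day 30 before it. The rule may not have been written with day 30 in mind. That is a fair doubt, although the table layout may be an artefact of text extraction. Section 11.5.2 does send a day-30 questionnaire, and 11.7 covers follow-up questionnaires without exception. If 11.7 does not apply, the primary-endpoint contact has no timed chase at all. Either reading calls for a clarification.

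**The primary outcome.** A reader might infer that every non-responder's primary outcome is collected out of window. The documents do not support this. Under 8.6.1 the outcome is a confirmed, datable event within a fixed 30-day period, so a contact on day 44 or 86 can still establish whether and when it happened. VTE is also assessed during admission, and readmission and outpatient data come from HES (11.5.2). CRF data must agree with source documents (16.1), which include medical notes and radiology reports (16.2, Source data). National linkage is planned (16.2, Use of Personal Identifiable Data). This objection largely stands. What remains is that the protocol does not say these records are the source of day-30 VTE status and date.

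**The questionnaire.** The form is not shown and the listed content need not be complete, so it cannot be said that it fails to ask about a new diagnosis.

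**EQ-5D-5L.** It may be taken at discharge, and participants followed by telephone or in clinic from the start are not subject to the 2-week wait. This stands and narrows the group affected.

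**Numbers, loss and bias.** One could apply an assumed non-reply rate to all 1512 participants: 10% to 40% would give 151 to 605. The protocol states no return rate, and 1512 includes people who die, remain in hospital, use the telephone or are seen in clinic, so this is not an estimate of those affected. Nor does any section say that a late responder is censored or counted against the 5% loss allowance in 15.3, or show that non-response depends on having had a VTE.

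**The 8-week step at later contacts.** Sent on the nominal date, it overruns those windows too, but as a last-resort retrieval step that is a reasonable choice, not an error.

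**Conclusion.** The point holds as a mismatch between two of the protocol's own rules. For a discharged participant followed by email or post who does not reply, the chase call comes 4 to 14 days after the day-30 window closes, and the other-source step lands inside the day-90 window. Day 30 is the only contact for which the telephone step cannot work from any send date inside the window.

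The consequence is limited. It falls mainly on EQ-5D-5L not taken at discharge, and on the dating of post-discharge VTE up to day 30 where records are not consulted. Bias in the primary estimate is not shown, and the number affected cannot be derived from the document. The verdict assumes that 11.7 covers the day-30 questionnaire and that forms go out inside the stated window. It is a cheap operational improvement, worth making because this contact carries the primary endpoint.

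**What to change.** Amend section 11.7 in two respects.

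1. **A separate escalation for day 30.** Telephone within a few days of non-response, and contact next of kin, the GP or the hospital by about day 35. For example, a form sent on day 30 and chased after 3 days gives a call on day 33, two days before the window closes. State that the 2-week and 8-week intervals apply only to the later contacts, where they can stay as they are.
2. **The source of VTE status.** State that VTE status and diagnosis date up to day 30 are taken from medical notes and radiology reports and from the planned linkage, whenever contact is made. A reply given before day 30 cannot cover the whole period, so the record check should run to day 30 for early responders as well.

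The cost is an amendment to one section. Calls already planned are made earlier, and sites spend a little time on record look-up from sources the protocol already names.
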